8.7 Efficacy Analysis

Efficacy analyses will be descriptive. The overall response rate will be summarized with frequencies and percentages. The duration of response for CR and PR patients will be summarized with descriptive statistics (N, mean, standard deviation, median, minimum, and maximum) as well as categorically. Response and duration of response will be determined using RECIST v1.1. Kaplan-Meier methodology will be used to summarize duration of response and PFS.

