2.2 Secondary Objectives

- To characterize the PK profile of single and multiple doses of intravenously administered FPA144 in patients with gastric cancer and in other solid tumors, including bladder cancer
- To evaluate the safety and tolerability of longer term exposure to FPA144 administered intravenously every two weeks
- To evaluate the objective response rate (ORR) in patients with FGFR2b-selected gastric cancer and other solid tumors by tumor type, including FGFR2b-selected bladder cancer (*Part 2 only*)
- To evaluate duration of response in responding patients with FGFR2b-selected gastric cancer and other solid tumors by tumor type, including FGFR2b-selected bladder cancer (*Part 2 only*)
- To characterize the pharmacodynamic profile of FPA144 through an analysis of the immune cell infiltrate in pre-treatment and on-treatment tumor biopsies by tumor type (*Part 2 only*)

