Patients enrolled in Part 1(A and B) or Part 2 of the study may continue treatment with FPA144 in 28-day cycles until disease progression, intolerable toxicity, patient or physician decision to discontinue, death, or termination of the study. Responding patients who discontinue treatment while still in response (CR, PR or SD) should get follow-up scans at 12-week intervals to determine the duration of response, unless other anticancer therapy is started.

All patients should return to the clinic for end-of-treatment (EOT) assessments irrespective of whether a patient is withdrawn or withdraws at a planned visit or mid-cycle.

During Part 1(A and B) and Part 2, AEs will be assessed as outlined in Section [6.2.1.1](#) below.

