8.5 Analyses of Tumor Response

Patients will be classified according to their best overall tumor response (complete response [CR], partial response [PR], stable disease [SD], or progressive disease [PD]). Frequencies, proportions, and exact 95% CI of patients, when appropriate, stratified by their best overall tumor response will be calculated. Patients with a best overall tumor response of CR or PR with duration of at least 4 weeks (28 days) will be further classified as having an objective tumor response. Listing of patients with an objective tumor response will be presented.

Duration of response will be calculated as the number of days from the first documentation of overall response (CR or PR) to the first documentation of disease progression or death, whichever comes first. Patients who are alive and progression-free at the time of data analysis will be censored at the time of their last assessment for tumor response.

Duration of stable disease will be calculated from Cycle 1, Day 1.

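### Duration of response is summarised by an ordinary mean, SD and median although ongoing responses are censored, which understates it and sets a second median beside the Kaplan-Meier one

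*Combined protocol and SAP*

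**What the plan says.** Duration of response is a Part 2 secondary objective (section 2.2): "To evaluate duration of response in responding patients with FGFR2b-selected gastric cancer and other solid tumors by tumor type". Section 2.5 lists it as a secondary endpoint.

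Section 8.5 defines it as a time to event: "Duration of response will be calculated as the number of days from the first documentation of overall response (CR or PR"), ending at progression or death. The same section sets the censoring rule. Responders who are alive and progression-free at the analysis "will be censored at the time of their last assessment for tumor response".

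Section 8.7 gives two summaries of this one variable. The first is "The duration of response for CR and PR patients will be summarized with descriptive statistics", listed as N, mean, SD, median, minimum and maximum, together with a categorical summary. The second comes at the end of the paragraph: "Kaplan-Meier methodology will be used to summarize duration of response and PFS".

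The documents do not say how a censored duration enters the mean, SD, median, minimum, maximum or categories, and they do not say which of the two medians is to be reported.

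**The concern.** The list of statistics in section 8.7 is the one that section 8.6 uses for body weight and vital signs, which are fully observed. Applied to durations that section 8.5 censors, it has two possible readings, and both are wrong. If censored times are counted as finished, every ongoing response is recorded as shorter than it is. If censored responders are left out, the responses most likely to be long are removed.

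Some censoring is to be expected. Under section 3.2 patients "may continue treatment with FPA144 in 28-day cycles until disease progression", so responses can still be running at the analysis. Follow-up scans for responders who stop treatment end once another anticancer therapy starts. Section 9.11 lets the sponsor close cohorts or the study at any time.

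The bias grows with longer responses and earlier data cuts. It is therefore largest when the Kaplan-Meier median has not been reached and the ordinary median is the only figure available to quote.

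**Working it through.** **The plan's own figure.** There is none to reproduce. The documents give no expected duration of response, event count or data-cut date.

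**Direction.** Let T be the true duration and C the follow-up after first response. The recorded time is min(T, C), which never exceeds T. The mean of recorded times is therefore below the mean of T whenever some responses are censored before they end. If none is censored, the bias is zero.

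**Size, in closed form.** Assumptions, none from the documents: T is exponential with median M, so the rate is λ = ln 2 / M. C is uniform on 0 to F months and independent of T.

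- Share censored: c = (1 − e^(−λF)) / (λF)
- Ordinary mean of recorded times: (1 − c) / λ, against a true mean of 1/λ
- Ordinary median m: solves e^(−λm) (1 − m/F) = 0.5

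For M = 6 and F = 12:

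- λ = 0.6931 / 6 = 0.1155, and λF = 1.386
- c = (1 − 0.25) / 1.386 = 0.541
- ordinary mean = 0.459 × 8.66 = 3.97 months; true mean 8.66
- m = 3.26 months; check: e^(−0.376) × (1 − 3.26/12) = 0.686 × 0.728 = 0.50. The true median is 6, so m is 46% too low.

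A category such as 6 months or longer fails in the same way. The recorded share is 0.50 × (1 − 6/12) = 25%, and the true share is 50%.

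Other settings by the same formulas:

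| True median | Maximum follow-up | Censored | Ordinary median | Too low by |
|---|---|---|---|---|
| 4 | 18 | 31% | 2.96 | 26% |
| 4 | 9 | 51% | 2.30 | 43% |
| 6 | 12 | 54% | 3.26 | 46% |
| 9 | 18 | 54% | 4.89 | 46% |
| 9 | 9 | 72% | 3.23 | 64% |

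**Simulation, 200 responders, 400 runs per setting.** True medians were 4, 6 or 12 months and maximum follow-up 6, 12 or 24 months. Censoring ran from 23% to 85%. The ordinary median was about 20% to 79% too low (3.18 against 4; 2.52 against 12), and the ordinary mean about 24% to 85% too low. Where the Kaplan-Meier median was typically reached, it came to 3.95–4.00 for a true 4, 5.99–6.06 for a true 6, and 11.91 for a true 12.

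**Leaving out censored responders.** In the setting with true median 6 and follow-up to 12 months, the mean of completed responses was 3.17 months against a true 8.7. This is worse than counting everyone.

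**A case of realistic size.** A full cohort of 30 at the 20% target in section 8.10 gives 30 × 0.20 = 6 responders. Suppose their durations are 2, 3+, 4, 6+, 8 and 10+ months, where + marks an ongoing response.

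- Ordinary mean: 33/6 = 5.5. Ordinary median: (4 + 6)/2 = 5.0.
- Kaplan-Meier: 5/6 = 0.833 at month 2; 0.833 × 3/4 = 0.625 at month 4; 0.625 × 1/2 = 0.313 at month 8. The median is 8.0.

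Under section 8.7 the report would show medians of 5.0 and 8.0 months for the same six patients.

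**The case against.** The strongest reply is that the right analysis is already there: section 8.5 defines the censoring and section 8.7 plans Kaplan-Meier. Section 8 is an outline, and a separate SAP is to give the detail before database lock. Efficacy is descriptive, and the two-stage rule in section 8.10 uses response counts, so no sample size, test or stopping rule depends on duration. These points stand. They limit the harm to reporting accuracy, but they do not correct the summary as written.

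It can also be said that the plan never states that censored times are treated as complete. That is true; it is silent. But a mean and SD do not come out of a Kaplan-Meier curve in the ordinary way, and neither counting nor dropping the censored times gives a valid result.

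The size is open to dispute. Longer follow-up shrinks the bias: with 0 to 36 months, the formulas above give medians 20% (true median 6) and 14% (true median 4) too low. Responses must also be confirmed after 4 to 6 weeks. If durations and follow-up both start at 1 month, true medians become 7 and 5. The main case then falls from 46% to 41%, and the 36-month cases to 18% and 12%. The range of 26% to 64% is therefore not a bound, but the direction does not change.

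Finally, numbers are small. Cohort A plans about 20 patients, so about 20 × 0.20 = 4 responders at the target rate. In simulations with 6 responders, the Kaplan-Meier median was not reached in 1% to 81% of runs. With light censoring (24%, true median 4) the two medians were close: 3.58 on average for the ordinary one, and 3.40 as the typical Kaplan-Meier value. At this size neither median is stable and the patient listing carries most of the information.

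**Conclusion.** The concern holds. Followed as written, section 8.7 gives a censored secondary endpoint an ordinary mean, SD and median that understate it, beside a Kaplan-Meier estimate that does not, with no rule on which to report.

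Under exponential durations with uniform, independent follow-up, the ordinary median is 26% to 64% too low for true medians of 4 to 9 months and maximum follow-up of 9 to 18 months, and still 12% to 18% too low in the most lenient 36-month cases. All these sizes rest on assumed durations and follow-up. The direction needs only that some responses are still ongoing at the analysis. With few responders and light censoring, the difference between the two medians may be small. Error rates and the go/no-go rule are unaffected, so this should be changed before the SAP is final but does not threaten the design.

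**What to change.** In section 8.7 and the SAP:

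- Delete the mean, SD and ordinary median of duration of response.
- Name the Kaplan-Meier median with its 95% confidence interval as the reported estimate, shown as not reached where that applies.
- Give the range with censored values marked, and flag ongoing responses in the listing of responders that section 8.5 already plans. A swimmer plot would do the same.
- If duration categories are kept, replace counts with Kaplan-Meier proportions at fixed times, and state that they are imprecise with 4 to 6 responders.

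This takes one or two sentences before database lock. It needs no new data and removes a table.

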8.8 Pharmacokinetic Analyses

Individual and mean (\pm SD) serum FPA144 concentration-time data will be tabulated and plotted by dose level. FPA144 PK parameters will be estimated from the serum study drug concentration-time data using a non-compartmental analysis (NCA) method with intravenous infusion input. Alternative methods may be considered. Estimated individual and mean (\pm SD) PK parameters will be tabulated and summarized by dose level. Other descriptive statistics might be reported for serum FPA144 concentration-time data and estimated PK parameters. Dose proportionality, study drug accumulation, and attainment of steady state will be evaluated as data allow.

The impact of immunogenicity on FPA144 exposure will be assessed.

8.9 Interim Analyses

No formal interim analysis of efficacy is planned. For Part 2 Cohorts A, C, D, E and F, an interim analysis of response may be performed to determine adequate efficacy.

Safety data will be reviewed on a routine basis by the Sponsor and CRO's Medical Monitors. In Part 1 (A and B), the Medical Monitors and Investigator(s) will review safety data from each dose cohort prior to dose escalation or de-escalation. Adverse event data from the extended treatment period will be presented to the Medical Monitors when available.

In addition, interim safety reviews will be conducted by an external Data Safety Monitoring Board (DSMB) on a regular basis throughout the treatment phase in Part 2. If warranted from these reviews, the DSMB may request additional safety data or recommend modification of study conduct as outlined in the DSMB Charter.

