8.10 Determination of Sample Size

Three patients per dose group, with a sample size increase to 6 in the case of DLT, is generally accepted as adequate to determine the safety of escalating doses of novel oncologic drugs. If a DLT is observed in 1 of 3 patients, then 3 additional patients will be enrolled at that same dose level. Dose escalation will continue until 2 of 3–6 patients treated at a dose level experience a DLT. The maximum tolerated dose (MTD) is defined as the maximum dose at which < 33% of patients experience a DLT during Cycle 1. After the MTD is determined, additional gastric cancer patients may be recruited at that dose level to further characterize the safety, PK, pharmacodynamics, and preliminary efficacy of FPA144.

In Part 1B, up to 30 patients with gastric cancer with or without FGFR2b overexpression, in the presence or absence of *FGFR2* amplification may be enrolled to explore preliminary long-term safety and PK.

In each of the Part 2 gastric cancer cohorts (Cohorts A, C, D, and E), approximately 30 gastric cancer patients with ranges of FGFR2b overexpression scores (IHC 3+ \geq 10%; IHC 0; IHC 2+ \geq

10% tumor membrane staining **and/or** IHC 3+ < 10%; IHC 1+ **and/or** IHC 2+ < 10%) will be enrolled and treated to further characterize safety and preliminary efficacy. For each cohort, a response rate of $\geq 20\%$ would be considered clinically meaningful. To ensure adequate efficacy, an interim analysis may be performed (with the assumption that a response rate of $\leq 5\%$ would be of no interest in the first stage). Assuming a significance level of 5% and 80% power (Table 5), the required sample size is 29 evaluable patients per cohort. The Sponsor may choose to suspend enrollment if no confirmed response (CR or PR) is observed after the first 10 evaluable patients have either received at least 4 cycles of therapy or have had disease progression, as it is unlikely the response rate would be 20% or more. If a full cohort of 30 patients is enrolled for a group, the precision of the 95% confidence interval for the response rate is within 18%.

Table 6: Parameters of Simon’s 2-stage Design

Targeted Response Rate	Response Rate of No Interest	Overall Sample Size	Sample Size at Stage I	Responses to go to Stage II	Number of Overall Responses
20%	5%	29	10	≥ 1	≥ 4

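### Section 8.10 quotes 5% level and 80% power for a two-stage rule whose first stage is optional; the attained level at 29 patients is 4.68% to 5.48%, and the figures do not describe the Cohort A size now planned

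*Combined protocol and SAP*

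**What the plan says.** Section 8.10 (Determination of Sample Size) treats a response rate of 20% or more as clinically meaningful and 5% or less as of no interest. It continues: "Assuming a significance level of 5% and 80% power (Table 5), the required sample size is 29 evaluable patients per cohort". Table 6 gives the design: 10 patients in stage I, at least 1 response to enter stage II, 29 overall, at least 4 responses overall. After Table 6, the same design is extended to each tumour type in Cohort F.

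The stage I rule is not mandatory. Section 8.10 says an interim analysis may be performed, and then: "The Sponsor may choose to suspend enrollment if no confirmed response (CR or PR) is observed after the first 10 evaluable patients". Section 8.9 (Interim Analyses) opens with "No formal interim analysis of efficacy is planned" and adds, for Cohorts A, C, D, E and F, that "an interim analysis of response may be performed to determine adequate efficacy".

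On cohort size, Section 8.10 and the synopsis (Statistical Procedures) still speak of about 30 patients in Cohort A. Sections 1.6, 4.1 and 4.4 and the synopsis (Study Design) now plan about 20. Cohorts B to E are closed. Cohort F is capped at 30 across all non-gastric tumour types. Section 8.7 states that efficacy analyses are descriptive.

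**The concern.** The error rates of a Simon design belong to the whole rule, including the stage I stop. If a cohort with 0 of 10 responses may go on, the requirement of 4 responses in 29 becomes, at the extreme, a single-stage test, which has both a higher false-positive probability and higher power. Section 8.10 therefore quotes operating characteristics for a rule that it does not commit to, and Section 8.9 adds doubt about whether stage I is part of the plan at all.

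The discretion would come into play often: with a true response rate of 5%, 0 of 10 is the most likely stage I result. At stake is whether a reader of the final report can attach the stated 5% and 80% to a count of 4 or more responses, and whether those figures apply to the cohorts actually being enrolled.

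**Working it through.** **Inputs.** From Section 8.10 and Table 6: p0 = 0.05, p1 = 0.20, n1 = 10, continue if X1 ≥ 1, n = 29, success if the total is ≥ 4, level 5%, power 80%. Sidedness is not stated. I take it as one-sided, which is usual for this design; the attained 4.68% would not fit 2.5% per side.

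**Formulas.**
- Stop applied: P(success) = Σ over x ≥ 1 of P(X1 = x; 10, p) × P(X2 ≥ 4 − x; n − 10, p).
- Stop never applied: P(X ≥ 4; n, p).
- The difference between the two is P(X1 = 0; 10, p) × P(X2 ≥ 4; n − 10, p).

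**Step 1: reproduce the plan's figure (n = 29, p = 0.05).**

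| X1 | P(X1) | P(enough responses in the next 19) | Product |
|---|---|---|---|
| 1 | 0.31512 | 0.06655 | 0.02097 |
| 2 | 0.07463 | 0.24529 | 0.01831 |
| 3 | 0.01048 | 0.62265 | 0.00652 |
| ≥ 4 | 0.00103 | 1 | 0.00103 |

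The sum is 0.0468. The same sum at p = 0.20 is 0.20485 + 0.27697 + 0.19843 + 0.12087 = 0.8011. The stated design reproduces. A grid search for the Simon optimal design at these inputs also returns 10/29 with cut-offs of 1 and 4.

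**Step 2: remove the stop at n = 29.**
- p = 0.05: P(0/10) = 0.95^10 = 0.599, and P(≥ 4 of 19) = 0.01324. The addition is 0.599 × 0.01324 = 0.0079, so the level rises from 0.0468 to 0.0548.
- p = 0.20: P(0/10) = 0.80^10 = 0.107, and P(≥ 4 of 19) = 0.5449. The addition is 0.0585, so power rises from 0.8011 to 0.8596.

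If a 0/10 cohort continues with probability q, the level is 0.0468 + 0.0079q. It passes 5% once q exceeds (0.0500 − 0.0468)/0.0079, or about 0.40.

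**Step 3: other sizes, keeping the 10-patient first stage and the cut-off of 4.**

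| n evaluable | Level, stop applied | Power, stop applied | Level, no stop | Power, no stop |
|---|---|---|---|---|
| 20 | 1.53% | 57.6% | 1.59% | 58.9% |
| 27 | 3.85% | 76.9% | 4.37% | 81.8% |
| 28 | 4.26% | 78.6% | 4.91% | 84.0% |
| 29 | 4.68% | 80.1% | 5.48% | 86.0% |
| 30 | 5.13% | 81.4% | 6.08% | 87.7% |

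Level and power both rise with n. With the stop applied, 29 is therefore the only size with level ≤ 5% and power ≥ 80%: 28 falls short on power and 30 exceeds the level. With no stop, 27 and 28 meet both.

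**The case against.** The strongest reply has five parts.

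- **Efficacy is descriptive.** Under Section 8.7 no hypothesis test is specified. Response is a secondary objective of a Phase 1 safety study, and 5% appears only as a sizing assumption. This stands and limits the consequence. It does not excuse quoting a level and power for a rule that is not fixed.
- **The excess is small.** At 29 it is at most 5.48 − 5.00 = 0.48 points, and only if every 0/10 cohort continues. This stands.
- **Thirty enrolled may mean 29 evaluable.** This also stands: the 30-patient figures assume that all 30 are evaluable and that the cut-off of 4 carries over, while Table 6 gives that cut-off only for 29.
- **Section 8.9 can be read as coherent.** Its two statements can mean that nothing formal is planned but an informal look is possible. That is fair within 8.9. The unresolved tension is with Table 6, whose stage I is a formal decision point.
- **A separate SAP may settle it.** Section 8 defers detailed methods to that document. It could, but the figures are stated here, and the rule they depend on should be stated with them.

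Two stronger readings are tempting and are not supported. A reader might infer that 5% holds only at exactly 29 patients with a binding stop. It does not: with the cut-off of 4, the level is at or below 5% at every size up to 29 with the stop and up to 28 without it. A reader might also infer that cohorts now enrolling carry an inflated false-positive risk. For Cohort A at about 20 the reverse is true, with a level of about 1.5–1.6%. In Cohort F a single tumour type reaches 29 only by taking nearly the whole allocation of 30.

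**Conclusion.** The point holds as an inconsistency of modest size. The quoted 5% and 80% are correct for the Table 6 rule at 29 evaluable patients with the stop applied (4.68% and 80.1%). They are not guaranteed by the plan as written, because the stop is discretionary and Section 8.9 disclaims a formal interim. Without the stop, the level is up to 5.48% and power 86.0%. At 30 evaluable patients the level would be 5.13% to 6.08%, on the assumptions noted above.

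For current enrolment the larger gap is power: at about 20 in Cohort A, the cut-off of 4 gives 57.6% to 58.9% against the stated 80%. All figures assume a one-sided exact binomial calculation, independent patients with a common response rate, and patient counts that are all evaluable. The documents do not support a claim that any cohort would be wrongly declared active, since they set out no such declaration.

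**What to change.** In Sections 8.9 and 8.10:

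1. State whether the 0/10 rule binds, and word 8.9 to match. If it binds, 8.9 should describe it as a planned stage I futility look instead of saying that none is formally planned.
2. Apply the cut-off of 4 responses to the first 29 evaluable patients only, and report later patients descriptively.
3. If the stop stays discretionary, restate the level as one-sided and up to 5.5% at 29.
4. Give the attained level and power for the sizes now planned, in particular Cohort A at about 20 and each Cohort F tumour type, or say that the Table 6 figures do not apply to them. Bring the Cohort A size in 8.10 into line with Section 4.1.

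The cost is a few sentences. The stated figures become slightly less favourable, and the lower power at 20 becomes visible. No extra patients are needed.

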8.10 Determination of Sample Size

Three patients per dose group, with a sample size increase to 6 in the case of DLT, is generally accepted as adequate to determine the safety of escalating doses of novel oncologic drugs. If a DLT is observed in 1 of 3 patients, then 3 additional patients will be enrolled at that same dose level. Dose escalation will continue until 2 of 3–6 patients treated at a dose level experience a DLT. The maximum tolerated dose (MTD) is defined as the maximum dose at which < 33% of patients experience a DLT during Cycle 1. After the MTD is determined, additional gastric cancer patients may be recruited at that dose level to further characterize the safety, PK, pharmacodynamics, and preliminary efficacy of FPA144.

In Part 1B, up to 30 patients with gastric cancer with or without FGFR2b overexpression, in the presence or absence of *FGFR2* amplification may be enrolled to explore preliminary long-term safety and PK.

In each of the Part 2 gastric cancer cohorts (Cohorts A, C, D, and E), approximately 30 gastric cancer patients with ranges of FGFR2b overexpression scores (IHC 3+ \geq 10%; IHC 0; IHC 2+ \geq

10% tumor membrane staining **and/or** IHC 3+ < 10%; IHC 1+ **and/or** IHC 2+ < 10%) will be enrolled and treated to further characterize safety and preliminary efficacy. For each cohort, a response rate of $\geq 20\%$ would be considered clinically meaningful. To ensure adequate efficacy, an interim analysis may be performed (with the assumption that a response rate of $\leq 5\%$ would be of no interest in the first stage). Assuming a significance level of 5% and 80% power (Table 5), the required sample size is 29 evaluable patients per cohort. The Sponsor may choose to suspend enrollment if no confirmed response (CR or PR) is observed after the first 10 evaluable patients have either received at least 4 cycles of therapy or have had disease progression, as it is unlikely the response rate would be 20% or more. If a full cohort of 30 patients is enrolled for a group, the precision of the 95% confidence interval for the response rate is within 18%.

Table 6: Parameters of Simon’s 2-stage Design

Targeted Response Rate	Response Rate of No Interest	Overall Sample Size	Sample Size at Stage I	Responses to go to Stage II	Number of Overall Responses
20%	5%	29	10	≥ 1	≥ 4

For Part 2 Cohort F, enrollment of patients with non-gastric solid tumors, including FGFR2b-selected bladder cancer, will be guided by the same 2-stage design used for cohorts A, C, D, and E for each tumor type.

However, the Sponsor may choose to close enrollment of a cohort at any time (Section 9.11). Based on Sponsor decision to close a subset of cohorts in Part 2 (as described in Section 4.1), the planned patient enrollment will be approximately 100 patients.

9. Ethical, Legal, and Administrative Aspects

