1.7 Clinical Experience with FPA144

This study was initiated in December 2014 and is the first-in-human assessment of the safety, tolerability and PK profile of FPA144. Dose escalation has been completed in patients with solid tumors (Part 1A) and gastric cancer (Part 1B) and the dose expansion phase (Part 2) is currently enrolling patients with FGFR2b-selected gastric and bladder cancer in this study.

Prior to completing Part 1A in November 2015, 19 patients with a variety of solid tumors were enrolled. Of these 19 patients, 18 completed at least one cycle and were evaluable for dose limiting toxicity. FPA144 was well tolerated in doses up to 15 mg/kg in patients with advanced solid tumors. There were no DLTs observed during dose-escalation and a MTD was not reached. Based on an assessment of safety, tolerability, and PK, a RD of 15 mg/kg was selected.

In parallel to Part 1A, escalating doses of FPA144 were also evaluated in gastric cancer patients in Part 1B. In Part 1B, a total of 8 gastric cancer patients were enrolled. One patient received FPA144 at 3 mg/kg, one patient at 6 mg/kg, and six patients at 10 mg/kg. Out of the 8 enrolled, 6 met both the criteria for FGFR2b overexpression by IHC and *FGFR2* amplification by FISH.

As of the latest data cut-off (October 28, 2016), a total of 53 patients across Part 1 (27 patients) and Part 2 (26 patients) have enrolled in the study and received at least 1 dose of FPA144. Of the 53 patients, 35 patients had gastric cancer and 18 patients were identified as having gastric cancer that was FGFR2b⁺ high (IHC 3+ intensity in $\geq 10\%$ of tumor cells). Of those 18 patients, 6 patients were enrolled in the Part 1B dose escalation and 12 patients in the Part 2 dose expansion Cohort A. In addition, 4 patients with gastric cancer with low FGFR2b overexpression have been enrolled into Cohort E and 10 patients with gastric cancer (IHC 0 – 2) have been enrolled into Cohort C in Part 2.

Safety and tolerability of FPA144 is supported by experience from a total of 53 patients from the Phase 1 study (FPA144-001) who have received at least 1 dose of FPA144. As of October 28, 2016, AEs have been reported in 48 of 53 patients (90.5%). Twenty-nine of the 53

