2.3 Exploratory Objectives

- To evaluate the stable disease rate and duration in patients with FGFR2b-selected gastric cancer and other solid tumors by tumor type, including FGFR2b-selected bladder cancer (*Part 2 only*)
- To assess progression-free survival (PFS) in patients with FGFR2b-selected gastric cancer and other solid tumors by tumor type, including FGFR2b-selected bladder cancer (*Part 2 only*)
- To explore the association between extent of FGFR2b overexpression and *FGFR2* amplification (or other molecular aberrations, as applicable) in tumor tissue and clinical outcome by tumor type

- To characterize the pharmacodynamic profile of FPA144 through an analysis of exploratory biomarkers in pre-treatment and on-treatment tumor biopsies by tumor type (*Part 2 only*)

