4.1 Planned Number of Patients and Study Centers

Part 1A (Dose Escalation): A total of 19 patients with locally advanced or metastatic solid tumors were enrolled.

Part 1B: A total of 8 patients with gastric cancer with or without FGFR2b overexpression, in the presence or absence of *FGFR2* amplification, were enrolled.

Enrollment in Part 1(A and B) is closed as the RD for Part 2 has been determined.

Part 2 (Dose Expansion): Part 2 is open for enrollment into the following cohorts:

- Cohort A: Approximately 20 patients with gastric cancer with strong FGFR2b overexpression.
- Cohort F: Up to 30 patients with FGFR2b-selected non-gastric solid tumors (including bladder cancer for which an accompanying validated IHC assay is available). Enrollment of additional tumor types will be contingent on the development of an accompanying validated laboratory test for the analysis of FGFR2b overexpression.

The following cohorts will be closed for enrollment in Part 2:

- Cohort B: Patients with gastric cancer with FGFR2b overexpression without FGFR2 amplification
- Cohort C: Patients with gastric cancer without FGFR2b overexpression
- Cohort D: Patients with gastric cancer with moderate FGFR2b overexpression
- Cohort E: Patients with gastric cancer with low FGFR2b overexpression

The study will be conducted at up to 35 investigational centers globally.

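### Section 8.10 and Table 6 still claim 29 evaluable patients, a 5% level and 80% power for gastric Cohorts C, D and E, which the protocol closes well short of that size

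*Combined protocol and SAP*

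**What the plan says.** **The design.** Section 8.10 assigns about 30 patients to each gastric cohort: "In each of the Part 2 gastric cancer cohorts (Cohorts A, C, D, and E), approximately 30 gastric cancer patients with ranges of FGFR2b overexpression". It continues: "Assuming a significance level of 5% and 80% power (Table 5), the required sample size is 29 evaluable patients per cohort". (The parameters are in Table 6; Table 5 lists laboratory tests.) A rate of 5% or less "would be of no interest in the first stage", and 20% or more is the target. Table 6 gives 10 patients in stage I, at least 1 response to continue, 29 patients overall and at least 4 responses in total. With no confirmed response in the first 10 evaluable patients the sponsor may suspend enrollment, "as it is unlikely the response rate would be 20% or more".

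**The efficacy look.** Section 8.9: "For Part 2 Cohorts A, C, D, E and F, an interim analysis of response may be performed to determine adequate efficacy". The synopsis statistics also still describe Cohort C (about 10 to 30 patients) and Cohorts D and E (about 30 each, at the sponsor's discretion).

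**The closures.** Section 4.1 says "The following cohorts will be closed for enrollment in Part 2" and names B, C, D and E. The synopsis design section and Section 1.6 agree. The end of Section 8.10 mentions the closures but revises only the total, to about 100.

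**Counts.** Section 1.7, at the 28 October 2016 cut-off: "4 patients with gastric cancer with low FGFR2b overexpression have been enrolled into Cohort E and 10 patients with gastric cancer" into Cohort C. It gives 12 patients in Cohort A and 26 in Part 2 as a whole.

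**The objective.** Section 2.3 keeps an exploratory aim, broken down by type of tumor: "To explore the association between extent of FGFR2b overexpression and *FGFR2* amplification (or other molecular aberrations, as applicable) in tumor tissue and clinical outcome by" …

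**The concern.** The current text contradicts itself. One part closes three cohorts; another part promises each of them about 30 patients and states operating characteristics that hold only at 29 evaluable. A reader who goes to the sample size section for the error rates behind a Cohort C or E result finds 5% and 80%, and neither applies.

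These cohorts matter because the synopsis presents Cohort C as a basis for exploring patient selection by FGFR2b expression, and D and E as a way to explore lower IHC limits. If their results are reported beside Section 8.10 as written, they will appear to come from a design with known error rates when they are small descriptive samples.

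**Working it through.** **1. The plan's own figure.** Inputs from Section 8.10 and Table 6: p0 = 0.05, p1 = 0.20, 10 patients in stage I (continue if at least 1 response), 29 in total (at least 4 responses). Sidedness is not stated; Simon's design is one-sided, and that is assumed.

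P(success | p) = Σ over x = 1 to 10 of P(Bin(10, p) = x) × P(Bin(19, p) ≥ 4 − x)

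- p = 0.05: 0.0468
- p = 0.20: 0.8011

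The 29 reproduces. The arithmetic is correct; it is attached to cohorts that will not reach that size.

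**2. How large the cohorts can be.**

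- At the cut-off: C = 10, E = 4, and D = 26 − 12 − 10 − 4 = 0. D is not stated in the protocol. Together: 14.
- Section 3.1.1 gives about 40 Part 2 gastric patients. Less about 20 in Cohort A, this leaves about 20.
- Section 8.10 gives a total of about 100. Less 19 (Part 1A), 8 (Part 1B), 20 (Cohort A) and 30 (Cohort F at its ceiling), this leaves 100 − 77 = 23.

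The range for the three cohorts together is therefore about 14 to 23. Taking 23 and the cut-off counts as minimums, the most any one cohort could hold is C: 23 − 4 = 19; E: 23 − 10 = 13; D: 23 − 14 = 9. All are below 29.

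**3. Operating characteristics at the cut-off sizes.** For each n, take the smallest r with P(Bin(n, 0.05) ≥ r) ≤ 0.05; power is P(Bin(n, 0.20) ≥ r). All enrolled patients are assumed evaluable. The upper limit for 0/n (two-sided 95%, exact) is 1 − 0.025^(1/n).

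| | n | Smallest r | Actual level | Power at 20% | 95% upper limit for 0/n |
|---|---|---|---|---|---|
| Cohort C | 10 | 3 | 1.15% | 32% | 30.8% |
| Cohort E | 4 | 2 | 1.4% | 18% | 60.2% |
| Cohort D | 0 | – | – | – | – |

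(At n = 10, r = 2 would have a level of 8.6%; at n = 4, r = 1 would have 18.6%.)

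**4. Sensitivity to later enrollment.** Cohort C at its maximum of 19 would need at least 4 responses (level 1.3%) and have 54% power. Even all three cohorts pooled fall short of 80%:

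- n = 14: r = 3, level 3.0%, power 55%
- n = 20: r = 4, level 1.6%, power 59%
- n = 23: r = 4, level 2.6%, power 70%

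**5. The stage I rule in Cohort C.** P(0/10 | 20%) = 0.8^10 = 10.7% and P(0/10 | 5%) = 0.95^10 = 59.9%. These are the stage I properties of the design itself, so ten evaluable patients are enough to apply that rule.

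**6. Who is in Cohort C.** The synopsis and Section 1.6 define Cohort C as IHC 0. Section 1.7 describes its 10 patients as IHC 0–2. In the synopsis, IHC 1+ belongs to Cohort E and IHC 2+ to D or E depending on percent staining. The two descriptions cannot both hold.

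**The case against.** The case for leaving this alone has substance.

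- **The cohorts were never all firm commitments.** The synopsis allowed Cohort C to stop at 10 and made D and E discretionary, and Section 8.10 lets the sponsor close any cohort. That stands as a reason for the small sizes. It does not justify keeping a 29-patient, 80% power statement for cohorts the protocol has closed.
- **Efficacy is descriptive.** Section 8.7 says so, Section 8.5 already provides exact 95% intervals where appropriate, and Section 8.9 plans no formal efficacy interim. This limits the harm. A reader might infer that 0/10 in Cohort C would be reported as a failed two-stage test supporting the IHC cut-off, but nothing in the protocol says that. Section 8.10 only permits enrollment to be suspended.
- **The counts are a snapshot.** The 10, 0 and 4 are cut-off figures, and the closures are in the future tense with no final numbers. This stands: they should not be written into the plan as closing sizes. The range in step 2 allows for it and does not change the conclusion.
- **Cohort C is not uninformative.** A reader might infer that the trial cannot judge activity at all outside strong expression. That goes too far: C has the stage I size, and the 10.7% risk of 0/10 at a true 20% rate is one the design already accepts.
- **No comparison between cohorts was planned.** The expression objective is exploratory, has no test or sample size, and is not restricted to Part 2, so Part 1B gastric patients also contribute. A reader might say the closures destroyed a powered contrast. They did not: even at 30 against 30, a two-sided Fisher test of 20% against 5% would have had about 24% power.

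It is also tempting to say that moderate expression has no patients. Given the IHC 0–2 description of Cohort C, that is not established.

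**Conclusion.** The concern holds as an inconsistency with a numerical consequence. The size and power stated in Section 8.10 and Table 6 do not apply to Cohorts C, D or E: on the protocol's own totals none can reach 29. Power at a true 20% rate is about 32% for C and 18% for E at the cut-off sizes, against the stated 80%, and nothing can be estimated for D if it stays empty. Cohort C can serve the stage I decision but not the full test.

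This rests on the cut-off counts, on D being zero by subtraction, on all enrolled patients being evaluable, on a one-sided 5% level, and on the approximate totals with Cohort F at 30. It does not show that the trial will misreport these cohorts, nor that the exploratory objective fails. Cohort A, planned at about 20 against 29, is a separate matter. The change should be made because the statement is wrong as written and easy to correct.

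**What to change.** At the next amendment, with the SAP to match:

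1. In Section 8.10, Table 6 and the synopsis statistics, remove Cohorts C, D and E from the 29-patient, 5%/80% statement, and correct the reference to Table 5.
2. Report each cohort's final count at closure with the exact 95% interval for its response rate. Use 10, 0 and 4 only if confirmed.
3. Label the three cohorts descriptive only, with no formal conclusion of activity or inactivity.
4. Remove C, D and E from the efficacy look in Section 8.9.
5. Reconcile Cohort C's definition (IHC 0 in the synopsis and Section 1.6, IHC 0–2 in Section 1.7) before summarising any result by expression.
6. State that the gastric part of the expression objective in Section 2.3 is a descriptive summary of response by IHC intensity and percent staining across all treated gastric patients, including Part 1B.

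The cost is wording; no new patients or data are needed. The downside is that the stated figures become less favourable.
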